## **XV. GOOD CLINICAL PRACTICES**

### **1. Role of GCP**

This trial will be conducted in compliance with Good Clinical Practice (GCP) regulations. The intent of these regulations is to safeguard subjects’ welfare and assure the validity of data resulting from the clinical research. The VA Cooperative Studies Program will assist Local Site Investigators (LSIs) in complying with GCP requirements through its Site Monitoring, Auditing and Resource Team (SMART) based in Albuquerque, NM. SMART serves as the Quality Assurance arm of CSP for GCP compliance. Study site personnel will receive a GCP overview at the study organizational meeting.

.SMART will provide training, manuals and materials to assist study personnel in organizing study files and will be available throughout the trial to advise and assist LSIs regarding GCP issues.

### **2. Summary of Monitoring and Auditing Plans**

#### **a. Monitoring Visits –**

- (1) Initiation visits at each site soon after study start-up
- (2) Subsequent monitoring will be conducted yearly thereafter
- (3) Final monitoring visit to each site during last year of study
- (4) Additional monitoring visits may be conducted as deemed necessary by study leadership or SMART.

#### **b. Audits**

- (1) Routine audits – independent site visits to one or more sites per year as determined by SMART.
- (2) For-Cause audits –independent audit of a site as requested by study leadership or CSP Central Office.
- (3) Audits may be scheduled or unannounced.

## **XVI. STUDY MONITORING AND AUDITING PLANS**

Protection of the rights and welfare of patients is a primary concern of CSP. In addition to the International Conference on Harmonisation (ICH) Good Clinical Practice Guidelines, this trial will be conducted in compliance with VA guidelines, the Declaration of Helsinki, and the applicable parts of the United States Code of Federal Regulations or local laws governing the conduct of good clinical studies.

### **A. Monitoring bodies**

Four external bodies will oversee the ongoing scientific and ethical conduct of the study including the Data Monitoring Committee, the CSPCC Human Rights Committee (HRC), the VA Central IRB and Clinical Monitors (SMART). In addition, at the mid-point of the study, the Cooperative Studies Scientific Evaluation Committee (CSSEC) will review the study.

By agreeing to participate in the study, the medical center delegates responsibility for global monitoring of the ongoing study to these four bodies. However, the Research and Development (R&D) and the Human Studies Committee of the local medical center may require the investigators to submit additional reports concerning the status of the study. Internal operational oversight (described in Section XVIII) will be conducted by the MAVERIC CSPCC, the CSPCRPCC and the Study Chairmen’s Office.

#### **1. Data Monitoring Committee**

The Data Monitoring Committee (DMC) will review the progress of the study and monitor adherence to the protocol, participant intake, outcomes, complications, and other issues related to participant safety. They will also monitor the assumptions underlying sample size calculations for the study and alert the investigators if they see substantial departures as the data accumulate. The DMC will be composed of experts in nephrology, cardiology, and clinical trials. The Study Chairmen will make nominations to the Director, Cooperative Studies Program, who will make the final selection for the Committee. The DMC will make recommendations to the Director of the Cooperative Studies Program as to whether the study should continue or be terminated. The DMC can consider participant safety or other circumstances as grounds for early termination, including either compelling internal or external

evidence of treatment differences or feasibility of addressing the study hypotheses (e.g. poor participant enrollment, poor adherence). The DMC will conduct an in depth assessment of safety and efficacy data every six months at which time the study biostatistician will provide the DMC with an interim summary report on the study status and on safety data for monitoring purposes.

2. Human Rights Committee

The Human Rights Committee (HRC) at the Coordinating Center may review the study at the request of the Coordinating Center Director in order to provide suggestions regarding study participants' protection.

3. VA Central IRB

The VA Central IRB provides expert ethical and scientific review of multi-site projects while ensuring local issues are addressed. The VA Central IRB performs full, expedited, exempt, and continuing review and provides waivers of HIPAA authorization as necessary and appropriate. The VA Central IRB meets monthly in person and/or by video or teleconference. The Study Chairmen will initially submit a principal investigator (PI) application which will include model documents such as the informed consent form and any waiver requests. Once approved, this application package will be sent to all potential participating sites who will be responsible for submitting their own local site investigator (LSI) applications. Once both the PI and LSI applications have been approved, the study is reviewed in accordance with local R&D Committee policies and the VA Central IRB is provided a copy of the site approval document for the study to begin at that site. Continuing reviews are done annually.

4. CSP Site Monitoring, Auditing and Resource Team (SMART)

The CSP Site Monitoring, Auditing and Resource Team (SMART), located in the CSPCRPCC in Albuquerque, will monitor the trial for compliance with Good Clinical Practices. GCP monitors from SMART will visit participating sites shortly after enrollment is initiated and subsequent monitoring will be conducted yearly thereafter to monitor investigator regulatory and protocol compliance and to evaluate research practices. SMART will provide an orientation to GCP at the study kick-off meeting and provide GCP tools to enhance compliance. Additionally, SMART will

conduct periodic routine audits throughout the course of the study and for-cause audits as requested by study leadership or CSP VACO

## **B. Monitoring adverse events (AEs) and serious adverse events (SAEs)**

Timely and complete reporting of safety information assists study management in identifying any untoward medical occurrence, thereby allowing: 1) protection of study patients' safety; 2) a greater understanding of the overall safety profile of the study interventions and therapeutic modalities; 3) appropriate modification of the study protocol; 4) improvements in study design or procedures; and 5) compliance with regulatory requirements.

The local Site Investigator will be responsible for the AE and SAE reporting requirements as described in this protocol and outlined below:

- Closely monitoring research subjects during the study for the development of new AEs and SAEs.
- Reviewing the accuracy and completeness of all AEs and SAEs reported.
- Reporting all SAEs to the CSPCRPCC and MAVERIC CSPCC within 72 hours of becoming aware of the event.
- Complying with VA Central IRB policies for reporting adverse events
- Implementing plans the Study Group and Executive Committee may develop in response to safety concerns.

### 1. Adverse events

Adverse events (AEs) are defined by the VHA Handbook 1058.01, paragraph 4 (a) as "An AE is any untoward physical or psychological occurrence in a human subject participating in research. An AE can be an unfavorable and unintended event, including an abnormal laboratory finding, symptom, or disease associated with the research or the use of a medical investigational test article. An AE does not necessarily have to have a causal relationship with the research. "

For the purpose of CSP 578, the study interventions are study IV fluids and oral NAC/placebo. Related events involve an assessment of the degree of causality (attribution) between the study interventions and the event. Site investigators will be asked to provide an assessment of

relatedness. All AEs with a reasonable causal relationship to the investigative treatment will be considered "related." A definite relationship does not need to be established.

Local site investigators, with assistance from their study coordinator, are responsible for collecting AE information regarding the subjects at their sites. During the study, data on adverse events will be collected spontaneously through patient reports, actively elicited during the angiography visit through open-ended questioning and examination, and gathered at the time of telephone contact and medical record reviews during the follow-up period. Related adverse event data will be collected from the time of consent to 35 days post angiography. If a patient receives care at a non-VA facility for an adverse event they experience, research personnel will obtain the requisite release of information form(s) from the patient and once received, acquire the pertinent medical records from the facility.

AEs related to the study intervention that are reported to research personnel will be recorded on an adverse event form and documented in source records (e.g., the electronic VA medical record and/or the subject's study record). In this way, the site creates a permanent record that provides information on the subject's clinical course while in the study.

Adverse events which develop into Serious Adverse Events, as defined below, will be reported as such and followed to resolution or stabilization.

## 2. Serious adverse events

Serious adverse events (SAEs) are a subset of adverse events defined in VHA Handbook 1058.01, paragraph 4(r) and 21 CFR 312.32(a), as follows:

**Definition of SAE from CFR 312.32 (a):** Serious adverse event. An adverse event or suspected adverse reaction is considered "serious" if, in the view of either the investigator or sponsor, it results in any of the following outcomes: Death, a life-threatening adverse event, inpatient hospitalization or prolongation of existing hospitalization, a persistent or significant incapacity or substantial disruption of the ability to conduct normal life functions, or a congenital anomaly/birth defect. Important medical events that may not result in death, be life-threatening,

or require hospitalization may be considered serious when, based upon appropriate medical judgment, they may jeopardize the patient or subject and may require medical or surgical intervention to prevent one of the outcomes listed in this definition.

**Definition of SAE according to VA Handbook 1058.01:** An SAE is an untoward occurrence in human research that results in death, a life-threatening experience, inpatient hospitalization, prolongation of hospitalization, persistent or significant disability or incapacity, congenital anomaly, or birth defect, or that requires medical, surgical, behavioral, social, or other intervention to prevent such an outcome.

All SAEs, as defined in VHA Handbook 1058.01, paragraph 4(r) and 21 CFR 312.32(a), will be collected, regardless of whether or not they are considered related to the study interventions. SAEs with a reasonable causal relationship to the study interventions and associated medications will be reported as "related." A definite causal relationship does not need to be established.

Local site investigators, with assistance from their study coordinator, are responsible for collecting SAE information regarding the subjects at their sites. SAEs will be collected from the time of consent through day 90 following the patient's index angiography procedure or the time of patient termination if before day 90. During the study, data on SAEs will be collected spontaneously through patient reports, actively elicited during the angiography visit through open-ended questioning and examination, and gathered at the time of telephone contact and medical record reviews during the follow-up period. If a patient receives care at a non-VA facility for a serious adverse event they experience, research personnel will obtain the requisite release of information form(s) from the patient and once received, acquire the pertinent medical records from the facility.

SAEs that are reported to research personnel will be documented in source records (e.g., the electronic VA medical record and/or the subject's study record). In this way, the site creates a permanent record that provides information on the subject's clinical course while in the study. Research personnel at the site will ask follow-up questions to determine the exact nature of the SAE and obtain appropriate medical records, if needed. Each SAE will be followed to resolution or stabilization or until the end of study participation.

*a. Expedited reporting of serious adverse events*

All SAEs must be reported to CSPCRPCC and MAVERIC CSPCC and entered into the EDC system within 72 hours of the local site staff becoming aware of the event. The site must notify MAVERIC CSPCC, Chair’s Office, and CSPCRPCC of the event by email upon entering the SAE into the EDC system. The SAE will also be documented in source records (e.g., the electronic VA medical record and/or the subject’s study record).

SAEs that are BOTH unanticipated AND related to the study interventions (administration study fluids or NAC/Placebo) will be reported, in writing, to the VA Central IRB within 5 business days of the local staff becoming aware of the event. In addition, any research deaths that are BOTH unanticipated AND related to the study interventions will be reported by telephone to the VA Central IRB immediately upon the local staff becoming aware of the death. Written notification to the VA Central IRB must follow within 5 business days of becoming aware of the death.

All other SAEs (i.e., SAEs that are either anticipated or unrelated to the study interventions), including deaths that are either anticipated or unrelated to the study interventions, will only be reported to the VA Central IRB at the time of Continuing Review (CR). Sites should maintain the individual participant CSP #578 AE Tracking Logs provided by SMART to facilitate this reporting.

If an event meets FDA reporting criteria, meaning it is serious, unexpected and deemed possibly related to the study drug it will be reported by the CSPCRPCC to the CRADO after review by the Study Pharmacist, Study Chairs, MAVERIC CSPCC Director, and CSPCRPCC Director.

If needed, as required under the Food and Drug Administration Investigational New Drug (IND) protocol, CSPCRPCC will report SAEs that are both related to study intervention and unexpected to the FDA no later than 15 days from when they are notified. If the SAE is a death or a life-threatening event, this notification will happen within 7 days.

*b. Monitoring of serious adverse events*

SAEs will be monitored throughout the study by the Data Monitoring Committee. The study pharmacist and study biostatistician will generate tabulations of AEs and SAEs and present a summary of all AEs and SAEs to the DMC on a schedule set by the DMC. The DMC will also determine when they should be unblinded to treatment assignment for the reviewing of adverse event data. The DMC will recommend to the CSRD Director whether the study should continue or be stopped for safety reasons. The DMC will also monitor the primary endpoint at pre-determined intervals and recommend to the CSRD Director whether the trial should be stopped for efficacy or futility. Summary reports from the DMC will be provided to the VA Central IRB. We believe that the independent DMC can effectively monitor the trial for safety, since it will regularly review all outcomes according to treatment assignment, and will also have access to statistical support to determine the significance of any observed differences.

## XVII. BIOSTATISTICAL CONSIDERATIONS

### A. Overview of design

#### 1. The analytic model

There are two primary hypotheses that will be tested: 1) peri-procedure infusion of sodium bicarbonate is superior to infusion of sodium chloride for the prevention of serious, adverse clinical events within 90 day of angiography and; 2) peri-procedure administration of oral N-acetylcysteine (NAC) is superior to placebo for the prevention of serious, adverse clinical events within 90 day of angiography. The study will enroll 7,680 subjects over 2.5 years and evaluate each subject 90 days after the intervention. Within each site, subjects will be randomly assigned to one of four combinations of study interventions: 1) bicarbonate and NAC placebo, 2) saline and NAC placebo, 3) bicarbonate and NAC and 4) saline and NAC.

The study design for the primary hypothesis is a 2 x 2 factorial design with a binary outcome - any of a selected list of important clinical events occurring within 90 days of study treatment including death, need for acute dialysis, and persistent change in SCr at 90 days of at least 50% from the baseline SCr. We denote the 90-day binary outcome as ‘MAKE-D’ (major adverse kidney events and death). The binary predictors are the interventions bicarbonate and NAC. The interaction term, bicarbonate\*NAC, represents the combination of these two interventions. The primary analysis starts with a logistic regression analysis with three binary predictors.

For the primary hypothesis, the model equation for the analysis is:

$$\text{MAKE-D} = \beta_1 * \text{Bicarbonate} + \beta_2 * \text{NAC} + \beta_{12} * \text{Bicarbonate} * \text{NAC} \quad \textbf{Model Equation}$$

where,  $\beta_1$ ,  $\beta_2$ , and  $\beta_{12}$  are the logistic regression beta coefficients.

The two main questions of interest that we will test for the primary hypothesis are:

- 1) Does bicarbonate reduce the incidence of MAKE-D?
- 2) Does NAC reduce the incidence of MAKE-D?

The power calculation for determining the total sample size depends only on these two main effect hypotheses. This means that the exploratory analyses do not have any associated power analyses. The primary analysis will -firstly test the significance of the interaction term, bicarbonate\*NAC. In the event of a non-significant interaction term at p=0.05 level, the regression model will be refitted without the interaction term. Otherwise, a stratified analysis will ensue where logistic models with single binary predictors for different levels of bicarbonate and NAC will be refitted. We will carry out the primary analysis by means of multivariable logistic regression without adjustment for any additional covariates.

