## **B. Randomization procedures**

All patients meeting eligibility criteria and providing informed consent will be randomized to each of the two study interventions (IV isotonic bicarbonate versus IV isotonic saline and NAC versus placebo). The 2 x 2 factorial design will result in four discrete treatment combinations (bicarbonate/NAC, bicarbonate/placebo, saline/NAC and saline/placebo). Patients will be allocated in a 1:1:1:1 manner to each of these four treatment combinations. Randomization will be accomplished using a permuted block scheme with block size set to provide equal distribution into these four possible treatment combinations. Some offset or variability will be inserted to prevent anticipation of the next treatment. Randomization will be stratified by study site. Stratification by site is necessary to account for local variation in processes of care including the type and volume of iodinated contrast media administered during angiography and site-specific differences in peri-procedural provider practices such as discontinuation of angiotensin converting enzyme inhibitors, angiotensin receptor blockers, and diuretics.

Study coordinators at each site will be responsible for obtaining a randomized treatment assignment for each eligible patient. A web-based randomization program will be provided to study sites for this purpose. This web-based program will be tested at each site prior to the start of the trial and will be reviewed, as per Center guidelines, by the CSP Clinical Research Pharmacy Coordinating Center (CSPCRPCC) and the MAVERIC CSPCC. At the time of subject enrollment, study coordinators will enter the Subject ID number and study site into the randomization program. The program will check that all eligibility criteria are met. If met, the program will select the first unused entry from the pre-specified list of random treatment assignments for the particular site. The lists are stored on a secure server at the CSPCRPCC. If the electronic system fails, the same process will be carried out by telephone and fax. In such instances, research personnel at the site will contact the CSPCRPCC for instructions on completing a manual randomization. The eligibility criteria will be verified by the CSPCRPCC. If eligible, the random treatment assignment will be provided to research personnel.

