#### Analytic reports

Analytic reports will provide the proportions, the differences among proportions, the odds ratios, and the 95% confidence intervals for each of the summary statistics. This will be followed by a report of the results of confirmatory analyses. The confirmatory exploratory analyses will add to the basic model, factors related to disease severity, demographic and anthropomorphic measures, and structural factors such as medical site. The regression modeling we shall employ will include a model with treatment by covariate terms to explore the possibility of treatment by covariate effects (that is, exploration of potential subgroup effects). We will test that results vary or do not vary significantly by medical site. Finally we will explore the effect of including site as a random effect by extending logistic regression to generalized linear models that treat site as a random effect.

[figure not shown]
Losses to follow up and missing data

We conservatively estimate that up to 3% of subjects may be lost to follow up before 90 days. The site coordinators will make every effort to locate such subjects including at least three telephone contact attempts and one registered letter. Research staff are permitted to mail a letter to the participant for the purpose of appointment scheduling/reminders or follow-up contact. If such efforts fail and we have no information indicating the outcome for these subjects, then we will exclude them from the primary analysis and then carry out a worst case analysis to confirm the result of the primary analysis.

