5.3.2. Absence of Interaction

In the event of a non-significant interaction term at $p=0.05$ level, the regression model will be refitted without the interaction term. This multivariable logistic regression model will include two binary predictors, and can be expressed as:

$$\text{Log (Odds (MAKE-D))} = \alpha + \beta_1 X_1 + \beta_2 X_2 \quad (\text{Model 2})$$

Where X_1 is the indicator for IV intervention (1=Bicarb, 0=Saline), and X_2 is the indicator variable for oral intervention (1=NAC, 0=Placebo).

The parameter β_1 will estimate the independent effect of Bicarb compared to Saline, and the parameter β_2 will estimate the independent effect of NAC compared to Placebo.

Efficacy of Bicarb relative to Saline will be tested as follows.

Null	$H_0: \beta_1 = 0$
Alternative	$H_a: \beta_1 \neq 0$

If the Wald Chi-square test has $p \leq 0.024$, then the null hypothesis will be rejected and alternative hypothesis accepted. If the 95% Confidence Interval of the Odds Ratio does not include 1 and $\beta_1 < 0$, we can conclude that Bicarb is superior to Saline, after adjusting for NAC and Placebo. Conversely, if the 95% Confidence Interval of the Odds Ratio does not include 1 and $\beta_1 > 0$, we can conclude that Bicarb is not superior to Saline, after adjusting for NAC and Placebo.

Similarly, efficacy of NAC relative to Placebo will be tested as follows.

Null	$H_0: \beta_2 = 0$
Alternative	$H_a: \beta_2 \neq 0$

If the Wald Chi-square test has $p \leq 0.024$, then the null hypothesis will be rejected and alternative hypothesis accepted. If the 95% Confidence Interval of the Odds Ratio does not include 1 and $\beta_2 < 0$, we can conclude that NAC is superior to Placebo, after adjusting for Bicarb and Saline. Conversely, if the 95% Confidence Interval of the Odds Ratio does not include 1 and $\beta_2 > 0$, we can conclude that NAC is not superior to Saline, after adjusting for Bicarb and Saline.

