5.3.4. Evaluating Covariate Effects

To explore the possibility of treatment by covariate effects, we will refit the model with a vector of covariates included in the model, expressed as

$$\text{Log (Odds (MAKE-D))} = \alpha + \beta_1 X_1 + \beta_2 X_2 + r[Z] \quad (\text{Model 7})$$

Where, $[Z]$ is the vector of factors indicating disease severity, demographic and anthropomorphic measures, and structural factors such as medical site. Factors identified not to be balanced between the intervention groups in section 5.2 will be evaluated.

Additionally, we will explore the effect of including site as a random effect by extending logistic regression to generalized linear models that treat site as a random effect.

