5.6.1. Futility Analysis

If requested by the DMC, a futility analysis that includes conditional **power** estimation will be conducted to determine the probability of observing a significant result assuming the distribution of future event rates from additional data from the second half of the study follow 3 scenarios. These assumptions are:

no-change scenario – future event rates are same as currently observed,
expected scenario – future event rates are as proposed in the protocol, and
extreme scenario – all new events at the currently observed rate are in the control group.

6. Sample SAS Code

```
proc genmod;  
class outcome Bicarb NAC;  
model outcome = Bicarb NAC/ error=bin link=logit type3;  
make 'parmest' out=parmest;  
run;
```

```
/*to get estimated odds ratios*/  
data parmest;  
set parmest;  
if df gt 0;  
OR=exp(estimate);  
low_OR=exp(estimate-1.96*stderr);  
hi_OR=exp(estimate+1.96*stderr);  
run;
```

```
proc print data=parmest label noobs;  
title 'Estimated Odds Ratios and 95% CIs';  
var parm level1 estimate stderr or low_OR hi_OR;  
format estimate stderr OR low_OR hi_OR 6.3;  
label  
parm='Parameter'  
level1='Level'  
estimate='Beta estimate'  
stderr='Standard Error'  
OR='Estimated OR'  
low_OR='Lower limit 95% CI'
```

hi_OR='Upper limit 95% CI';
run;

7. Data Monitoring Committee Reports

Data and study progress will be monitored by the study executive committee and by the Data Monitoring Committee. The DMC will review the study progress and safety semiannually with additional meetings and communications as needed.

All reports will be generated in conjunction with the Data Management department using SQL and SAS.

Updated Shell tables can be found on Sharepoint using the following link

<https://vaww.ord.research.va.gov/CSP/Boston/csp578/centralfile/Data%20Monitoring%20Committee/Forms/AllItems.aspx?RootFolder=%2fCSP%2fBoston%2fcsp578%2fcentralfile%2fData%20Monitoring%20Committee%2f6%2e%20DMC%20Reports%20Shell%20Tables&FolderCTID=&View=%7b2F07C9DC%2d37B3%2d456C%2dAFDC%2d7F19514038EE%7d>

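### If 90-day event rates differ between sites, the primary test, which leaves out the site strata used in randomisation, is slightly conservative

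*Protocol*

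**What the plan says.** **Design.** Protocol VII.B allocates patients 1:1:1:1 by permuted blocks. It states "Randomization will be stratified by study site" and gives the reason: "Stratification by site is necessary to account for local variation in processes of care". Its examples are contrast type and volume, and local habits in stopping certain drugs around the procedure.

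**Deciding test.** Protocol XVII.A.1 carries out the primary analysis "by means of multivariable logistic regression without adjustment for any additional covariates". SAP 5.3.2 says of Model 2: "This multivariable logistic regression model will include two binary predictors". Model 1 (5.3.1) adds only their product, and Models 3 to 6 (5.3.3) have one treatment term each. The sample code in SAP section 6 is "model outcome = Bicarb NAC/ error=bin link=logit type3". The interim test in SAP 5.6 uses Model 2 at p ≤ 0.001, and the final test uses p ≤ 0.024.

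**Where site does enter.** Protocol XVII.H (Analytic reports) plans models that add medical site among other factors and a check on whether results vary by site. It ends: "Finally we will explore the effect of including site as a random effect". SAP 5.3.4 lists site among the Model 7 covariates and says "we will explore the effect of including site as a random effect by extending logistic regression". None of these analyses decides a primary hypothesis. No reason is given for leaving the stratum out of the test that does.

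**The concern.** Blocking within site balances the arms on site-level risk, so differences between sites contribute almost nothing to the chance variation of the treatment comparison. A logistic model without site does not know this. Its standard error is computed as if patients had been randomised with no strata. If site risks differ, that standard error is larger than the actual sampling SD of the estimate. The test then rejects a true null less often than stated and gives up some of the precision that stratification was meant to provide.

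At stake are a little power and the match between design and analysis. In a borderline result, the unadjusted test would decide while the analysis that follows the randomisation remained exploratory.

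**Working it through.** **Inputs from the documents.** Event rates 8.70% and 6.52% (difference d = 0.0218, mean p = 0.0761); 7,450 evaluable and 7,680 enrolled patients; 3% loss; 90% power; final two-sided level 0.024, so z = 2.257; 33 VA sites plus 12 non-VA sites.

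**Assumed, because the documents are silent.** Site intercepts are normal on the logit scale with SD 0.3, 0.5 or 0.7. The 10th to 90th percentiles of site rates are then about 5.1–10.4%, 3.8–12.3% and 2.7–14.2%.

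**1. The plan's own figure.** The two-proportion formula with pooled null variance gives 7,342 at level 0.025 and 7,406 at 0.024, both within 2% of 7,450. The loss adjustment is 7,450/0.97 ≈ 7,680. Power at 7,450 and level 0.024 is 90.2%. The stated size is reproduced.

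**2. Share of outcome variance due to site.** f = Var(site rate)/[p(1−p)], with p(1−p) = 0.0761 × 0.9239 = 0.0703. Under site-stratified allocation the true SD of the unadjusted estimate is r = √(1−f) times what the model reports.

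**3. True size.** Size = 2[1 − Φ(2.257/r)].

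**4. Power at 7,450.** Null SE s0 = √[4p(1−p)/7,450] = 0.006144. Alternative SE s1 = √[2(0.0870×0.9130 + 0.0652×0.9348)/7,450] = 0.006139.
- Planned test: Φ[(d − 2.257·s0)/(r·s1)]
- Site-stratified test: Φ[(d − 2.257·r·s0)/(r·s1)]

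**5. Patient equivalent.** The extra N at which the planned test, under the same stratified allocation, reaches the stratified test's power at 7,450.

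| Between-site SD | f | SE too large by | True size | Power, planned | Power, stratified | Patients |
|---|---|---|---|---|---|---|
| 0 | 0 | 0 | 0.0240 | 90.2% | 90.2% | 0 |
| 0.3 | 0.6% | 0.3% | 0.0235 | 90.3% | 90.4% | 31 |
| 0.5 | 1.8% | 0.9% | 0.0227 | 90.4% | 90.7% | 88 |
| 0.7 | 3.7% | 1.9% | 0.0214 | 90.6% | 91.3% | 179 |

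The stratified column assumes that all between-site variance is removed. A random-intercept fit only approximates this, so the gains are if anything slightly high.

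**6. Simulation check under the null.** Settings: 33 sites of unequal size, 7,450 patients, blocks of 8 (assumed), event rate 8.7%, main-effects Wald test at 0.024, 200,000 trials per setting. Rejection rates were 0.0240, 0.0233, 0.0223 and 0.0186 at SD 0, 0.3, 0.5 and 1.0, with Monte Carlo error of about 0.0002. Step 3 at the same 8.7% rate gives 0.0240, 0.0235, 0.0226 and 0.0183. With 45 sites and 8,420 patients the simulated rates were 0.0237, 0.0234, 0.0223 and 0.0184. The test was not anti-conservative in any setting.

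**The case against.** The strongest reply is that little is at risk. The unadjusted model is prespecified consistently in both documents and is the test the trial was sized for: protocol XVII.F equates it, with one term, to a chi-square test on a 2 × 2 table. Any error is in the safe direction, power stays at or above 90%, and site-adjusted analyses are already planned. All of this stands, and it is why the point is minor.

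The effect is also conditional. Protocol VII.B describes differences in care between sites, not in MAKE-D rates. If the rates do not differ, nothing is lost. A reader might infer that the real error rate is simply below the stated level; the documents do not establish that.

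A reader might also multiply f by 7,680 and claim about 50, 141 or 285 patients. That compares a stratified test with an unadjusted test under unstratified randomisation. The planned test already benefits from stratified allocation, so the gain over it is 31, 88 or 179.

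Nor should one expect the adjusted model to print a smaller standard error. In a small simulation (33 sites, SD 0.5, 200 trials), adding site moved the mean SE from 0.0901 to 0.0910 and the log odds ratio from −0.303 to −0.310. The gain comes through the ratio of the two: 0.303/0.0901 = 3.36 against 0.310/0.0910 = 3.41.

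**Conclusion.** The mismatch is real: a stratum that the protocol calls necessary is absent from the primary and interim tests, with no reason given. The consequence is small and depends on unknown between-site variation. For an assumed SD of 0.3 to 0.7, size falls from 0.024 to between 0.0235 and 0.0214, and the power forgone is about 0.1 to 0.7 percentage points. Larger effects need strong differences between sites: at SD 1.0, with 10th to 90th percentile site rates of about 2–19% around 8.7%, size would be about 0.018.

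A stronger reading, that the primary test is invalid or the trial underpowered, is not supported. Omitting the stratum does not inflate type I error, a positive result from the planned test stands, and power is not below the stated 90%. This is a minor efficiency and consistency point.

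**What to change.** Name one method. Make the random-site-intercept logistic model of SAP 5.3.4 the primary test in protocol XVII.A.1 and SAP 5.3.1–5.3.3, and the interim test in 5.6, at the significance levels already set. Keep unadjusted Model 2 as the sensitivity analysis, and still report the marginal proportions and their differences as SAP 5.3 promises. Change the procedure named in SAP 5.3 and the code in section 6 to match.

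The cost is wording and code; site is already recorded. There are two small downsides to state in the SAP:
- The odds ratio becomes conditional on site, so it lies slightly further from 1 and its reported SE need not shrink.
- Data per site are sparse at the interim: 292 events over 45 sites is about 6.5 per site if all are active. The 5.3.3 models each use half the sample. Both favour a random intercept over fixed site terms.

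If the sponsor prefers the unadjusted test, one sentence saying why, and accepting that it may be slightly conservative, would settle the matter.
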